**Aim 1: Evaluate RIMO's direct effect on linkage to MAT, length of time on MAT, dropout, and total days of MAT.**

H1: Relative to the control group, RIMO will have a direct effect on: a) initiating MAT sooner, b) staying on medication longer, c) reducing dropout, and d) receiving more total days of MAT.

**Aim 2: Evaluate RIMO's direct and indirect (via MAT) effects on time to relapse, opioid use, and opioid-related overdose.**

H2: RIMO will have direct and indirect (via days of MAT treatment) effects on: a) time to relapse, b) days of opioid use, and c) number of overdoses.

**Aim 3: RIMO's direct and indirect (via MAT and opioid use) effects on opioid-related fatalities, OUD symptoms, physical health, mental health and the cost of health care utilization.**

H3: RIMO will have direct and indirect (via days of MAT treatment and days of opioid use) effects on: a) opioid-related fatalities, b) opioid use disorders symptoms, c) physical health, d) mental health, and e) cost of health care utilization.

Referral Only Control. During the phase 1 pilot, we collaborated with our study partners as well as the Illinois Opioid STR partners to develop a brochure that includes a list of MAT providers in Chicago, and their location, telephone number, hours of operation, adjacent bus lines, and type of funding accepted (e.g., Medicaid). In addition, the brochure includes a range of other SUD treatment options (e.g., residential or outpatient drug-free treatment), including office-based physicians who prescribe buprenorphine or other forms of MAT. This brochure is will be given to participants in both groups at the baseline assessment. Research staff will follow a script that does not include any statements regarding motivation for treatment. At present, based on our interviews with key informants and focus group with pilot study participants, there is currently no systematic method in place for referring individuals to MAT (or other SUD treatment) either from the first responders following administration of naloxone or at the EDs following their admission for opioid-related overdose. Hence, this condition represents more than the “usual care” in the community.

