Direct Effects of RIMO on MAT (Aim 1). Relative to the referral only control group, the direct effects of RIMO on reducing dropout and receiving more total days of MAT will be evaluated using a multilevel structural equation modeling (MSEM) with mixed effects in MPlus (version 7.4). The analysis will model observations (Level 1) nested within participants (Level 2), with participants modeled as a random factor anchored on the baseline version of the dependent variable. Randomization to RIMO will be modeled as a Level 1 predictor. We will check for the need to use models that adjust for counts or zero saturation.

Direct Effects of RIMO on Secondary Outcomes of Time to Relapse, Opioid Use and Overdose (Aim 2) and Death, OUD, Health, Mental Health, and Health Care Utilization (Aim 3). Relative to the referral only control group, the direct effects of RIMO on time to first relapse (H2) will be evaluated with a survival analysis similar to Aim 1 H1. It will be examined after the point of randomization and after each follow-up interview. The direct effects of RIMO on days of opioid use (H2), opioid overdoses (H2), opioid-related fatality (H3), symptoms of OUD (H3), physical health problems (H3), mental health symptoms (H3), and the cost of health care utilization (H3) will also be evaluated using a series of MSEM with mixed effects in MPlus modeled in the same way as above. Most of the above variables are relatively continuous, but we will check for the need to use models that adjust for counts or zero saturation. For opioid-related fatality (H3), we will define the dependent variable as dichotomous in MPlus (equivalent to using logistic regression).

Indirect Effects of RIMO (Aims 2 and 3). To evaluate indirect effects, we will determine the extent to which the direct effects of RIMO on the above dependent variables are changed by of days of MAT received (H2 & H3) and/or days of opioid use (H3) using the Preacher and colleagues framework for testing mediation in MSEM with REML in MPlus. Loss of statistical significance in the path coefficient from the intervention conditions to the other outcome variables would indicate full mediation; a reduction in the path coefficient would indicate partial mediation. Change will be evaluated using MacKinnon's joint-significance testing of the path *z*-scores with a Sobel test using a standard error based on bootstrapping and criteria of  $p < .05$  on the degree of change.

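### The H2 and H3 'direct effects' are estimated without the mediators, so they are total effects, and the plan does not say which estimate decides the direct half of these hypotheses

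*Combined protocol and SAP*

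**What the plan says.** - **Hypotheses (Section 1).** H2 reads "RIMO will have direct and indirect (via days of MAT treatment) effects on" time to relapse, opioid use and overdose. H3 reads "RIMO will have direct and indirect (via days of MAT treatment and days of opioid use) effects on" fatality, OUD symptoms, health and cost. Table 2.1 (Section 2) marks MAT days as a mediator for H2 and H3, and days of opioid use as a mediator for H3.
- **First step (Section 10, direct effects).** The Aim 1 model nests observations in participants and anchors on the baseline value of the outcome. On the arm it says: "Randomization to RIMO will be modeled as a Level 1 predictor". The H2 and H3 outcomes other than relapse "will also be evaluated using a series of MSEM with mixed effects in MPlus modeled in the same way as above". Time to relapse "will be evaluated with a survival analysis similar to Aim 1 H1", which is a Cox model with assignment as the main predictor.
- **Second step (Section 10, indirect effects).** The mediators now enter: "we will determine the extent to which the direct effects of RIMO on the above dependent variables are changed by of days of MAT received", with days of opioid use added for H3. The reading rule is: "Loss of statistical significance in the path coefficient from the intervention conditions to the other outcome variables would indicate full mediation". A smaller coefficient is read as partial mediation. Joint-significance and bootstrapped Sobel tests are planned.
- **Power (Section 4).** Power is stated for the tests of direct effects and for the indirect effects. None is stated for RIMO's path after adjustment for the mediators.

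**The concern.** In a hypothesis that contrasts direct with indirect effects, the direct effect is the part that does not pass through the mediator. The first-step models contain no mediator, so they cannot isolate that part. Their RIMO coefficient is the sum of both parts.

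Aims 2 and 3 turn on this split: does linkage support do anything for use, overdose or health beyond getting people onto MAT? If the first-step result is taken at its label, the direct half of H2 or H3 is decided by the wrong quantity. The second step can then call the same outcome fully mediated. Both statements would follow the plan, and nothing in it says which one settles the hypothesis.

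**Working it through.** **1. What each step estimates.** Let X be arm, M days of MAT and Y the outcome, with M = aX + error and Y = c'X + bM + error. Then:

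- first step (no M in the model): RIMO coefficient = c = c' + ab, the total effect;
- second step (M in the model): RIMO coefficient = c', the direct effect.

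If RIMO works only through MAT, c' = 0 and c = ab. The first-step test is then a test of ab, under the label of a direct effect.

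**2. The plan's own power figure.** Section 4 claims 80% power at d=0.2 with an effective n of 429 to 398 per group. Its formula is n' = O/(1 + ICC(RM-1)), with O = 175 + 0.94 x 175 x 3 = 668.5 and RM = 4:

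- ICC 0.13: 668.5/1.39 = 481;
- ICC 0.34: 668.5/2.02 = 331.

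The stated 429 and 398 are not reproduced. The last step is: 398 per group gives 80.5% power, 429 gives 83.4%, and 393 are needed for 80%. The mismatch is a separate matter and does not decide this point, so the illustration covers all these values and the floor of 175 people.

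**3. Illustration under full mediation.** The documents give no values for a or b, so these are assumptions. Two pairs give a total effect of size 0.2 with c' = 0: 0.5 x 0.4 and 0.8 x 0.25. Each setting was simulated 2,000 times by ordinary regression with unit within-arm variances, independent observations, no baseline covariate and no mediator-outcome confounding. Full mediation was counted when the first step was significant, the adjusted path was not, and both mediator paths were.

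| n per group | Source of n | First step significant | Adjusted RIMO path significant | Labelled full mediation |
|---|---|---|---|---|
| 175 | people randomised | 46-47% | 6% | 43-44% |
| 331 | formula, ICC 0.34 | 73-74% | 4-5% | 71% |
| 398 | stated | 80-81% | 4-5% | 78-79% |
| 429 | stated | 82-84% | 5-6% | 79-81% |
| 481 | formula, ICC 0.13 | 87% | 5% | 84% |

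Closed-form check of the first step: at n=175, 0.2/sqrt(2/175) = 1.87 and P(Z > 1.96 - 1.87) = 46%; at n=481, 0.2/sqrt(2/481) = 3.10 and the power is 87%.

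Where the first step was significant, the second step gave the full-mediation label in 93% (0.433/0.466 at n=175) to 98% (0.794/0.814 at n=398) of trials.

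**4. Sensitivity.** With total d=0.1 (0.5 x 0.2) the first step is significant in 16-34% of trials over the same n; with d=0.3 (1.0 x 0.3), in 79-99.5%. The adjusted path stays at about 5%.

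**5. Why loss of significance cannot replace an estimate.** If a true direct effect of d=0.2 were tested with the precision of a simple two-group comparison at n=175, it would be non-significant in 100 - 46 = 54% of trials. A non-significant path does not show that the direct effect is absent.

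**6. Time to relapse.** The mediation paragraph covers all the preceding outcomes but describes only MSEM and gives no survival version. Table 2.1 counts MAT days over 9 months, while relapse is timed from randomisation, so MAT days can accrue after relapse has occurred.

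**The case against.** The plan uses the word consistently in a looser sense. H1 says "Relative to the control group, RIMO will have a direct effect on" four MAT outcomes and has no mediator, so there 'direct effect' means the randomised comparison. Read that way, Section 10 is ordinary two-step mediation: estimate the arm effect, add the mediators, see what remains. The first step is a valid intent-to-treat test, and the second obtains the mediator-adjusted path.

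Much of this stands, and it rules out three stronger readings that a reader might infer.

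- *That no mediator-adjusted analysis is planned.* It is, in the paragraph that follows.
- *That 46-87% is the chance of a false final report.* These figures are the power of a valid total-effect test under assumed path sizes. The second step would usually label such trials fully mediated.
- *That indirect effects are tested only if the first step is significant.* Section 10 states no such gate. Only the full or partial label refers to the RIMO path's significance.

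What does not stand is the loose reading for H2 and H3. There the plan itself opposes direct to indirect, so the word has to mean the path outside the mediator.

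**Conclusion.** The point holds as a mislabelled and undefined estimand, not as a missing analysis. The first-step models for H2 and H3 estimate total effects; the adjusted path that answers the direct half is obtained later but never named as the direct effect, and no rule says which estimate decides. Under full mediation with total d=0.2, the two candidate tests disagree widely: about 46-87% significant against about 5%. That gap rests on assumed values of a and b and on a simplified simulation. The labelling conclusion needs only the text. The gap is widest for time to relapse, where no mediation model for a survival outcome is given. This is a cheap improvement that changes what H2 and H3 can conclude.

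**What to change.** 1. In Sections 4 and 10, call the first-step tests for H2 and H3 total (intent-to-treat) effects. Leave the hypotheses in Section 1 as direct and indirect.
2. In Section 10, define the direct effect for H2 and H3 as RIMO's coefficient in the planned with-mediator model. Report it with a confidence interval, and base the direct conclusion on it rather than on loss of significance.
3. State that this estimate assumes no unmeasured mediator-outcome confounding, because MAT days are not randomised; the same applies to days of opioid use in H3.
4. For time to relapse, either specify a mediation model that counts only MAT days before relapse, or limit the claim to the total effect.

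Items 1 to 3 cost only wording, since the models are already planned. Item 4 needs either a new model specification or a narrower claim. The price in interpretation is that direct-effect estimates will be smaller when part of the benefit runs through MAT. They also tend to be less precise the further the arms separate on MAT days, and they lack the protection of randomisation that the total effect keeps.

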### 4. Sample size and power calculation

We plan to recruit and randomize 350 participants over 24 months. There should be 99% or more power to determine the direct effect of RIMO on the primary outcome of time to MAT initiation (H1a) assuming a sample size of 350 patients, randomized into two groups of 175 each, interviews at 4 time points for the main analysis (baseline, and 3, 6, and 9 months post-randomization), our average completion rate of 94+% per follow-up wave, and a moderate to large effect size of  $d=3.0$ . This expected effect size was based on the natural log of the odds ratio ( $\text{Log}^e(\text{OR})=d$ ) of initiating MAT ( $\text{OR}=20.2$ ) from RIMO Pilot study ([name] et al., under review). For the other tests of direct effects, the effective n for power calculations in repeated measures analysis varies between a lower bound of the number of unique people per group ( $N=175$  people), and an upper bound of the number of people randomized plus the completed follow-up interviews or 668 observations per group ( $O=(175 \text{ people at intake} + \text{average of } 94\% \times 175 \text{ people} \times 3 \text{ follow-ups})$ ) as a function of the intra-class correlation coefficient (ICC) associated with the individual and the number of repeated measures (RM) per person ( $\text{effective } n'=O/(1+\text{ICC}(\text{RM}-1))$ ). In our prior studies, ICC of the other dependent

variables ranged from .13 to .34. Thus the effective n= range from 429 to 398 per group and be capable of detecting an effect size of  $d=0.2$  or more with 80% power for a two-tailed test of  $p<.05$  of effect sizes  $d=.2$  or more. For mediation analysis, the tests should also have 80%+ power for a 2-tailed test of  $p<.05$  and an indirect effect size of  $d=.2$  or more.

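### The 80% power at d=0.2 in Section 4 cannot apply to opioid-related fatality (H3a), and Section 10 leaves its model ambiguous

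*Combined protocol and SAP*

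**What the plan says.** Section 4 divides the tests into two groups. The primary outcome, time to MAT initiation (H1a), has its own power figure, for participants "randomized into two groups of 175 each". Everything else comes under one statement, which begins "For the other tests of direct effects, the effective n for power calculations in repeated measures analysis varies between" a lower bound of 175 people and an upper bound of 668 observations per group. It concludes: "Thus the effective n= range from 429 to 398 per group and be capable of detecting an effect size of" d=0.2, with 80% power, two-tailed, at p<.05. Fatality is not named, not excluded, and given no separate power or expected death rate.

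Aim 3 in the protocol summary lists opioid-related fatalities as H3a, with a hypothesised direct effect of RIMO. Table 2.1 in Section 2 defines the outcome as any of a list of ICD-10 causes of death in CDC death records.

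Section 10 lists fatality with days of opioid use, overdoses, OUD symptoms, health and cost as outcomes for the multilevel model already described for Aim 1. That model has observations nested within people, with "participants modeled as a random factor anchored on the baseline version of the dependent variable". A later sentence says of fatality that "we will define the dependent variable as dichotomous in MPlus (equivalent to using logistic regression").

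**The concern.** The 80% figure depends on each person contributing several observations. Death contributes one. If the sentence in Section 4 is read as written, the plan claims for its most serious outcome a power that the design cannot deliver at that effect size. A null result on deaths could then be read against a claimed 80% power and taken as evidence that RIMO does not affect mortality.

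The model text raises a second, smaller problem. A baseline anchor and a participant random factor make sense for an interview measure taken four times. Neither has a role for death, and the plan does not say that they are left out.

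**Working it through.** **Inputs.** From Section 4: 175 per group; d=0.2; two-sided alpha 0.05; effective n of 398 to 429; and the conversion ln(OR)=d, which the plan uses to turn OR 20.2 into d=3.0. From Table 2.1: one yes/no value per person, taken from death records, so interview completion does not alter n. The control death risks used below are assumptions.

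**1. The plan's own figure.** For two means, power = Φ(d·√(n/2) − 1.960).
- n=398: 0.2 × √199 = 2.821, and Φ(0.861) = 80.5%.
- n=429: 0.2 × √214.5 = 2.929, and Φ(0.969) = 83.4%.
- 80% needs 393 per group.

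So the 80% follows from the stated effective n. (Whether 398 to 429 follows from the stated ICCs is a separate question and does not affect this point.)

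**2. The n that applies to death.** With one value per person there are no repeated measures to raise n, so the plan's own lower bound of 175 applies. Even for a continuous outcome, 0.2 × √87.5 = 1.871, and Φ(−0.089) = 46.4%. At 175 per group, 80% power needs d of about 0.30.

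**3. A yes/no outcome at d=0.2.** Power = Φ((|p₁−p₂| − 1.960·SE₀)/SE₁), where SE₀ is the pooled and SE₁ the unpooled standard error, with 175 per group. I took the maximum over all control risks, so the ceiling needs no assumed death rate.

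| Conversion of d=0.2 | Implied OR | Maximum power |
|---|---|---|
| ln(OR)=d (the plan's own) | 0.82 (1/1.22) | 15.2%, at a control risk of about 52% |
| ln(OR)=1.65d | 0.72 (1/1.39) | 33.7%, at about 54% |
| ln(OR)=d·π/√3 | 0.70 (1/1.44) | 39.4%, at about 55% |
| Cohen's h=0.2 | varies with risk | 46.4% (arcsine formula, as in step 2) |

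Worked example, first row: p₁=0.525 gives p₂=0.475, a difference of 0.0500. SE₀=0.05345 and SE₁=0.05339. (0.0500 − 0.1048)/0.05339 = −1.03, and Φ = 15.2%.

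**4. At lower, assumed control risks.**

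| Control risk | ln(OR)=d | ln(OR)=d·π/√3 | Deaths halved |
|---|---|---|---|
| 2% | 4% | 6% | 12% |
| 4% | 5% | 9% | 19% |
| 8% | 7% | 13% | 35% |
| 10% | 8% | 15% | – |

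Cohen's h stays at about 38% to 45% over 2% to 10%, but only because it then stands for a very large relative effect: from 2% down to about 0.2%, or from 10% to about 4.8%. Fisher's exact test at 2%, 5% and 10% gives less than the normal approximation: about 2%, 4% and 6% with ln(OR)=d, and 2%, 6% and 11% with d·π/√3.

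**5. What 80% would take.** At a 10% control risk, a fall to 2.7% (odds ratio about 4 against control). At 5%, a fall to 0.23% (about 22). At 3%, even no deaths in the RIMO group gives only 64%.

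**6. The model.** Everyone is alive at baseline, so the baseline version of the outcome is the same for all and carries no information. With one record per person, a participant random effect cannot be identified. The sentence on dichotomous coding sets the outcome type; it does not say that these two terms are removed.

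**The case against.** Section 4 never says that fatality has 80% power. Its paragraph is framed around repeated measures, with ICCs from earlier studies, and it names 175 as the lower bound of effective n. A reader might infer an explicit claim of 80% power for deaths. The documents support only coverage by implication: the opening words take in every other direct-effect test, H3a is one, and nothing excludes it. The fault is a missing exception in a general sentence.

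A reader might also infer that no yes/no outcome in this trial could exceed 39% power. That is not so. The ceiling holds only at d=0.2, and larger effects have more power, as step 5 shows. The 39% also depends on the π/√3 conversion, which is not in the documents: the plan's own conversion gives 15%, and Cohen's h gives 46%.

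Nor do the documents support the reading that the fatality model cannot be fitted. Section 10 itself moves fatality to a logistic-equivalent analysis, and a logistic model with one record per person and no baseline term can be fitted. What stands is that the text does not say so.

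Finally, trouble from sparse data, such as an infinite odds ratio when one group has no deaths, depends on a death rate that the plan does not give. It is a risk to provide for, not a demonstrated failure. Fatality is also one of several secondary outcomes, and the power for the primary outcome is untouched.

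**Conclusion.** The point holds in limited form. The 80% at d=0.2 does not apply to opioid-related fatality at any death rate. With 175 per group, power at d=0.2 is below 50% on every conversion tried, with a ceiling of 15% to 46%. The ceiling rests only on 175 per group, two-sided 0.05, and one value per person. The lower range of about 4% to 15% further assumes control risks of 2% to 10% and an odds-ratio conversion. Halving deaths at assumed risks of 2%, 4% and 8% gives about 12%, 19% and 35%.

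On the model, the finding is an ambiguity: Section 10 does not drop a baseline anchor that is constant or a random factor that one record per person cannot identify.

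**What to change.** In Section 4, state that the 80% at d=0.2 does not apply to opioid-related fatality, and give the range above with its assumed control risks and conversions.

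In Section 10, state that fatality is analysed with one record per participant, without baseline anchor or random factor. Report deaths by group with a confidence interval, using a method valid for sparse events; exact or Firth-penalised logistic methods would both serve, and the choice is the sponsor's. Add that a null result on deaths is not to be read as evidence of no effect. H3a can remain a stated hypothesis.

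The cost is wording in two sections and a less favourable stated power for one secondary outcome. No new data or design change is needed.

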## **2. Primary and secondary objectives and outcome measures**

The primary outcome measure for the study is the GAIN-Quick Version 3 (GAIN-Q3). The GAIN-Q3 includes 4-6 symptom count screeners that are correlated .9 or more with the 11 to 43-symptom version in the full GAIN. It also has cut points with excellent (~90%) sensitivity, specificity, and area under the curve (AUC) relative to the full GAIN in 9 problem areas related to substance use disorders, physical health, internalizing and externalizing mental health disorders, as well as school, work, stress, HIV risk behaviors/victimization, and crime/violence. The days of use measures have been validated against the Timeline Follow-back, collateral reports, and urine and saliva tests. The GAIN-Q3 also includes summary measures for health care utilization, functional impairment, quality of life, and life satisfaction. The GAIN-Q3 includes the behavioral health screener and health care utilization measures that have been recommended by NIH's Phenx common data elements as two of the most reliable, valid, efficient, and inexpensive tools in the field. At each follow-up, the Q3 follow-up will be supplemented with a) a section on overdose and naloxone experiences, and b)

symptom counts from the OUD scale. Table 2.1 crosswalks the key independent measures and secondary outcomes from the hypotheses to their definitions, reliability, data sources, and the specific aims they address.

Table 2.1. Crosswalk of Variables, Definition, and Aims	H1	H2	H3
Experimental Assignment: Based on computer-generated urn randomization, participants will be assigned to the referral only control group or the experimental RIMO condition.	R	R	R
MAT Time to Initiation: Days from index naloxone administration to the initiation of any kind of MAT, from treatment records.	O		
Length of Staying on Medication: Days between MAT initiation and discharge, from treatment records.	O		
MAT Days: Total days of MAT over 9 months from GAIN-Q3 and treatment records.	O	M	M
Time to Relapse: Days from randomization to next subsequent use of opioids or heroin based on GAIN Q3 follow-up interviews and urine tests.		O	
Opioid Days of Use: Days of opioids and/or heroin use summed over the GAIN-Q3 follow-up interviews.		O	M
Opioid Overdose: Number of opioid-related overdose[s] summed over the GAIN-Q3 follow-up interviews.		O	

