The Research Manager will then use gRand Urn Randomization (Version 1.10) to randomly assign 350 participants to one of the two conditions: referral to MAT control or RIMO. Urn randomization adjusts the probability of assignment to condition in ways that simultaneously minimize differences in multiple stratification variables. The base rate will be set to 50% of each condition and adjusted over time to simultaneously balance on multiple participant characteristics (gender, race, age, community) and baseline measures of key outcomes including days of opioid use in the prior 90 days, lifetime number of overdoses, high severity (3+ symptoms) on lifetime OUD, health problems, mental health symptoms, and high quarterly health care costs (more than \$7,600 dollars). The Research Manager will enter the information into the program, generate the assignment, inform participants of their group assignment, and describe the next steps. Research interviewers will be kept blind to the condition assignment for study participants.

Participants assigned to the "Referral Only" group will receive a brochure that includes a list of MAT providers in Chicago, and their location, telephone number, hours of operation, adjacent bus lines, and type of funding accepted (e.g., Medicaid). In addition, the brochure includes a range of other SUD treatment options (e.g., residential or outpatient drug-free treatment), including office-based physicians who prescribe buprenorphine or other forms of MAT. The brochure will be given to participants in both groups at the baseline assessment. Research staff will follow a script that does not include any statements regarding motivation for treatment. At present, based on our interviews with key informants and focus group with pilot study participants, there is currently no systematic method in place for referring individuals to MAT (or other SUD treatment) either from the first responders following administration of naloxone or at the EDs following their admission for opioid-related overdose. Hence, this condition represents more than the "usual care" in the community.

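### The mediation models name no covariate beyond arm and the baseline outcome, so indirect effects through days of MAT and opioid use could be created, inflated or hidden by a shared baseline cause

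*Combined protocol and SAP*

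**What the plan says.** All references are to the combined protocol and SAP.

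- **Model terms.** Section 10 describes the multilevel structural equation models in its paragraph on direct effects: "Randomization to RIMO will be modeled as a Level 1 predictor", with "participants modeled as a random factor anchored on the baseline version of the dependent variable". The secondary outcomes are to be modelled in the same way.
- **Mediation step.** The paragraph on indirect effects (Section 10) begins "To evaluate indirect effects, we will determine the extent to which the direct effects of RIMO on the above dependent variables are changed" and adds days of MAT (H2 and H3) and/or days of opioid use (H3). It then applies joint-significance and Sobel tests at p<.05. It names no further covariate, no assumption about mediator-outcome confounding and no sensitivity analysis.
- **Interpretation rule.** "Loss of statistical significance in the path coefficient from the intervention conditions to the other outcome variables would indicate full mediation" (Section 10).
- **Mediator.** Table 2.1 in Section 2 defines days of MAT as "Total days of MAT over 9 months from GAIN-Q3 and treatment records", so it is measured after randomization.
- **Baseline data available.** Section 8 has the urn balance the arms on gender, race, age, community and "baseline measures of key outcomes including days of opioid use in the prior 90 days, lifetime number of overdoses", together with OUD severity, health problems, mental health symptoms and health care cost. These are balancing factors. Section 10 does not name them as model covariates.

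**The concern.** RIMO is randomized; days of MAT and days of opioid use are not. Randomization supports the arm-to-mediator effect and the arm-to-outcome effect. It gives no support to the mediator-to-outcome path, which is the other half of every indirect effect.

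People who stay on MAT may differ at baseline in severity, mental health or overdose history, and those traits may also affect later opioid use, overdose, symptoms and cost. If such a trait is left out, its influence is attributed to the mediator and multiplied by RIMO's effect on that mediator.

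Two features of the design do not prevent this. Urn balancing makes the arms alike, but this confounding acts among people within an arm. The participant random effect does not help either: arm is constant within a person, so the indirect effect rests on the between-person association of mediator and outcome.

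Indirect effects are named in H2 and H3, so they are stated hypotheses. Under the interpretation rule, confounding could turn a lost arm coefficient into a claim that RIMO works entirely through MAT.

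**Working it through.** **The plan's own figure.** Section 4 states 80% or more power for an indirect effect of d=.2. It cannot be reproduced, because no arm-to-mediator or mediator-to-outcome path values are given. The calculation below therefore illustrates size under stated assumptions.

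**Inputs**
- From Section 4: 350 participants, 175 per arm.
- Assumed: the true effect of the mediator on the outcome is zero.
- Assumed: one baseline cause U has standardized effect r (0.2, 0.3 or 0.4) on both mediator and outcome, with the same sign.
- Assumed: the baseline outcome is in the model and correlates c = 0.3 to 0.6 with U.
- Assumed: RIMO moves the mediator by a = 0.5 to 1.66 within-arm SD. The top value is the pilot odds ratio for any MAT (summary, Phase 1) on the d scale: ln(20.2) × √3/π = 3.006 × 0.551 = 1.66. It concerns any MAT at 30 days in 33 people, not MAT days over 9 months, so it serves only as an upper limit.

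**Formula.** With unit variances within arm, regressing the outcome on arm, mediator and baseline outcome gives the mediator a spurious coefficient

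b* = r²(1 − c²) / (1 − r²c²),

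and the spurious indirect effect is a × b*.

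| r | b* at c=0.3 | b* at c=0.6 | lowest a×b* (a=0.5, c=0.6) | highest a×b* (a=1.66, c=0.3) |
|---|---|---|---|---|
| 0.2 | 0.0364/0.9964 = 0.037 | 0.0256/0.9856 = 0.026 | 0.01 | 0.06 |
| 0.3 | 0.0819/0.9919 = 0.083 | 0.0576/0.9676 = 0.060 | 0.03 | 0.14 |
| 0.4 | 0.1456/0.9856 = 0.148 | 0.1024/0.9424 = 0.109 | 0.05 | 0.25 |

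Simulated means agree with these values to within about 0.01 SD.

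**False positives (Sobel test, same settings, simulated).** About 6-12% at r=0.2, 15-33% at r=0.3 and 44-80% at r=0.4. With U added to both equations, the estimate returns to about 0 and the rejection rate to about 3-5%.

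**Joint-significance test, smaller arm effects.** A separate simulation used a = 0.3 to 0.8 SD and gave the baseline outcome its own effect of 0.3 on the outcome. It rejected in about 7-12%, 20-40% and 56-86% of runs at the same three values of r. With a = 0 it rejected in at most about 5%, so a false indirect effect also needs RIMO to move the mediator. H1d and the pilot MAT days (11.2 vs 0.76) anticipate that it will.

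**Where the bias goes.** In that second simulation, at a=0.5, r=0.4 and c=0.3, the indirect effect was 0.074 and the arm coefficient with the mediator in the model was −0.076. The two cancel, so the total arm effect is untouched and only its division into direct and indirect parts is wrong.

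**Direction.** If U acts with opposite signs on mediator and outcome, b* becomes negative, and a true beneficial indirect effect would be reduced or masked.

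**No baseline version of the outcome.** Here c = 0 and b* = r² (0.04, 0.09, 0.16), so the partial protection is lost. These are continuous-outcome, person-level approximations and do not carry over exactly to a dichotomous fatality outcome or a survival model.

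**The case against.** Five objections deserve weight.

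1. **Silence is not exclusion.** A reader might infer that the plan rules out further adjustment. It does not: it names no other covariate, and the baseline-anchoring sentence is carried over from the direct-effects paragraph. For the survival analyses, Section 10 allows covariates if needed, and time to relapse is analysed in a similar way. This stands as to wording. An optional, unspecified allowance is still not a pre-specified adjustment for mediation.

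2. **Baseline adjustment already helps.** This is correct. At r=0.4 and a=1.0, false positives fall from about 85% with no baseline outcome to 76% at c=0.3, 50% at c=0.6 and 21% at c=0.8. The bias shrinks but does not vanish.

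3. **The size is assumed.** Also correct. A reader might infer that even weak confounding yields a large false indirect effect. At r=0.2 the spurious effect is at most about 0.06 SD. Within the ranges used, it passes the plan's d=.2 only near the top: at r=0.4 and c=0.3, a must exceed 0.2/0.148 = 1.35 SD.

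4. **The sign is assumed.** The documents do not establish it, so a reader cannot conclude that indirect effects would be exaggerated. They might equally be hidden.

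5. **These are secondary, explanatory analyses.** This stands, and it limits the severity. A reader might infer that the trial's main conclusions are compromised. They are not, because the arm comparisons do not use the mediator-to-outcome path.

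**Conclusion.** The point holds as a gap in the mediation analysis. As written, the models test a non-randomized path with no named protection beyond the baseline outcome, and for fatality and time to relapse not even that exists. Following the plan could give a biased indirect effect in either direction.

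Under the stated assumptions the harm ranges from slight (shared cause of 0.2) to serious (0.4, where roughly half to four-fifths of null mediators would pass a Sobel test). The documents do not show where in that range the trial would fall. The figures rest on a single shared cause of the same sign and on a person-level simplification of the planned multilevel model.

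The primary outcome and all intent-to-treat comparisons are unaffected. Severity: should-fix.

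**What to change.** In Section 10, under indirect effects:

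1. Add to both the mediator and the outcome equations the baseline variables already collected for the urn: gender, race, age, community, 90-day opioid days, lifetime overdoses, OUD severity, health problems, mental health symptoms and health care cost. Pre-specify a reduced set for sparse outcomes such as opioid-related fatality.
2. Add a sensitivity analysis that reports, for each indirect effect, the residual mediator-outcome correlation that would reduce it to zero.
3. State that indirect effects rest on an assumption of no unmeasured mediator-outcome confounding, which randomization does not guarantee.

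A RIMO-by-mediator interaction is an optional check; it addresses a different assumption.

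The cost is SAP wording, a few model terms and some analysis time, with no new data. Measured covariates cannot remove unmeasured confounding, which is why the second and third items are needed as well as the first. The change should be made before outcome data are analysed.
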